## **Analysis of Safety Outcomes**

The primary safety endpoint and the secondary safety endpoints will be analyzed in two ways. For each type of event, the percentage of people who experience the event at least once will be compared using the chi-square test. Logistic regression models will be performed to adjust for the covariates such as age, pre-existing CAD and pre-existing diabetes. In addition, a similar analysis will be done for all AE and SAE that are possibly or probably attributable to the study intervention. An event-based analysis will also be done since adverse events can be recurrent. In this analysis, a non-parametric method called the mean cumulative function (MCF) will be used as an alternative to the above crude incidence rate analyses. The overall safety profiles as well as the safety profiles in specific subgroups will be compared for the two randomization groups including the times of event recurrence and censoring mechanisms.

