This is the second phase of a multi-center trial of ACS patients. The first phase was a safety study involving 31 patients and was completed in December 2012. US Food and Drug Administration (FDA) reviewed the safety and efficacy data from the first phase and approved proceeding to this phase. In this trial, 128 participants will be randomized in a 1:1 ratio to either initial LDL-apheresis and an oral daily dose of 40-80mg of Atorvastatin or equivalent (ILLT group) vs. a daily dose of 40-80mg of Atorvastatin or equivalent without LDL-apheresis (SMT group) following an uncomplicated PCI. Intravascular ultrasound with virtual histology (IVUS-VH) derived coronary atheroma volume and composition will be obtained at baseline and 90 days after enrollment, while peripheral blood sampling will be performed at enrollment, and at 24 hours, 30 days, and 90 days post-PCI, along with a four-month and a six-month clinical follow-up visits to determine whether the ILLT group will affect:

1. The total number of and percentage of patients with major peri-PCI procedure adverse events (primary safety endpoint)

2. The total number of and percentage of patients with statin-related abnormal liver function test events and statin-related muscle injury events (secondary safety endpoint)
3. The total atheroma volume within a ≥ 20 mm long segment of the target coronary artery at 90 days IVUS-VH follow-up (primary effectiveness endpoint)
4. The %NC component within a ≥ 20 mm long segment of the target coronary artery at 90 days IVUS-VH follow-up (secondary effectiveness endpoint)
5. The EPC-CFU/ml of peripheral blood, compared to SMT group from baseline to 30 days and 90 days post-PCI (secondary effectiveness endpoint)
6. The major adverse CV events (MACE) at 90 days and at six months follow-up (secondary effectiveness endpoint)

2. Background and Significance

2(a) Background

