4(c)(v)(2). Randomization and Blinding Procedures: Following an uncomplicated PCI procedure, patients who are eligible and willing to participate in the study will be randomly assigned to either the ILLT or SMT arm using an automated telephone-based randomization system. A touch-tone phone is necessary to use this Voice Information System (VIS) to randomize eligible subjects. CSPCC will assign each site a unique 6-digit PIN that the unblinded staff can use to access the VIS system and randomize a subject (or add/update an SSN). The VIS will query the unblinded staff for subject information and confirm these data prior to determining the subject's treatment group assignment. A copy of the appropriately executed consent and HIPAA authorization documents must be on file at the Hines CSPCC within 24 hours of randomization. If the VIS is not working during normal business hours, the research coordinator can telephone the Hines CSPCC staff to randomize a patient. The subjects or Site Investigators will not be blinded to the study treatment assignment; however all follow-up visits and endpoint adjudications will be performed by a dedicated study nurse blinded to treatment allocation. Patients will be cautioned not to reveal his/her treatment allocation to the blinded study nurse. This blinding precaution will be emphasized by the

procedures written into the study Operations Manual and the communications to the Site Investigator, the Site Coordinator and other study personnel during the kick-off meeting and the teleconference calls throughout the study. Patients will be screened and consented before PCI, but will have the opportunity, after PCI, to decline participation in the study and will not be randomized if they choose not to participate.

4(d) Intervention and Treatment

The randomized treatment regimens of this study include:

- (i) ILLT
- (ii) SMT

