4(f)(iv). AE and SAE Monitoring and Reporting: AE/SAE/UADE will be monitored at the study sites throughout the whole period of the study at each clinic visit and telephone contact, beginning as soon as a study participant signs the Informed Consent and continuing through end-of-study for each participant. All AE/SAE/UADE including both those related to the study intervention and those not related to the intervention, will be collected and recorded on the appropriate case report forms (CRF). For the purpose of safety monitoring, the study intervention is defined as the use of 1) statins with or without the addition of LDL-apheresis, 2) LDL-apheresis, and 3) follow-up cardiac catheterization and IVUS-VH as described in this protocol.

All SAEs require expedited reporting. The SAE report form should be completed and faxed to CSPCC/CSPCRPCC/Study Chair Offices within 48 clock-hours of initial awareness of the event. The CSPCRPCC AE Pharmacist will be responsible for evaluating all serious adverse events for patient safety concerns. In addition, a Clinical Events Committee (CEC) will be formed to adjudicate adverse events in the study. The committee involves a physician from CSPCC, a Q.A./safety monitor from CSPCC, and the AE Pharmacist from CSPCRPCC. The committee is independent from the Study Chair and the Site Investigators.

Serious adverse events that are related to the investigative treatment and unexpected will be reported to the FDA, CSP Director, and Site Investigators after review by the Study Chair, the CSPCRPCC Director and the CSPCC Director. Site investigators should follow local policy to inform their IRB. The Hines CSPCC will generate tabulations of all AE/SAE/UADE for the Data Monitoring Committee annually

or on a more frequent schedule if requested by the Committee. All participants presenting to the VA hospital will be provided treatment for all SAEs and UADEs.

While participants have the right to withdraw from the study at any time, they will continue to be monitored, via passive follow-up, for SAEs that occur within 30 days of leaving the study. All unresolved SAEs must be followed up at least every 30 days until resolved or when no further change is expected. All SAEs are followed until no changes are expected or follow-up ends on the last study participant, regardless of the participant's status in the trial.

4(g) Biostatistical Considerations

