## **Plan for Presenting Data to DMC**

Hines CSPCC will produce a progress report every six months for review by Data Monitoring Committee. The report will include figures for patient accrual, tables for baseline characteristics, site performance, data quality, treatment compliance, and safety issues.

The frequency, reasons and timing for withdrawal from the study will be reported and compared by treatment group. The number of misrandomized patients, i.e. ineligible patients who were randomized will be reported by treatment group. The reasons for misrandomization will be listed. The number of patients who do not receive a study intervention, receive the wrong study intervention in error or intentionally receive the study intervention to which they were not randomly assigned will be reported by treatment group. Protocol deviations will also be compared by surgical site.

---

	ILLT		SMT		
Withdraw	N	%	N	%	p-value
Reason ---					
Too ill to participate					
Timing ---					
Post-PCI					
30-day follow-up					

---

Protocol Deviation	# of Protocol Deviation			# of Patients with Deviations		
	ILLT	SMT	ALL	ILLT	SMT	ALL
Miss-randomization F/U outside window						

The mean group change from baseline to follow-up visits of outcome measures will be compared between the two treatment groups using a two-sample t-test:

Outcomes	Time	ILLT		SMT		Change	
		N	Mean±SD	N	Mean±SD	%Chg	p-value
Atheroma V	Baseline 90-day F/U						

AE and SAE will be analyzed by preferred term and system organ class. Additionally, incidence rates for AE and SAE will be analyzed by investigator attributed relatedness and severity of the events with the similar table format as the following:

AE/SAE	ILLT		SMT		p-value
	# of Event	% of Patient	# of Event	% of Patient	
AE					
SAE					

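### Beyond the named safety endpoints and MACE, the final AE/SAE incidence comparison is specified only for events judged attributable, with no statement that attribution is blind to arm

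*SAP*

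**What the plan says.** - **Final safety analysis.** SAP, Analysis of Safety Outcomes, and Protocol 4(g)(vi) compare the primary and secondary safety endpoints by chi-square and logistic regression, event type by event type. They then add that "a similar analysis will be done for all AE and SAE that are possibly or probably attributable to the study intervention". MACE is compared separately with no attribution filter. An event-based mean cumulative function (MCF) analysis and a comparison of overall safety profiles follow, but the events they cover are not defined.
- **What counts as the intervention.** Protocol 4(f)(iv): "the study intervention is defined as the use of 1) statins with or without the addition of LDL-apheresis, 2) LDL-apheresis, and 3) follow-up cardiac catheterization", the third item also taking in the repeat IVUS-VH. This is given for safety monitoring. The SAP uses the term without defining it. Protocol 1(c) describes the control arm as statin without apheresis.
- **Who knows the arm.** Protocol 4(c)(v)(2): "The subjects or Site Investigators will not be blinded to the study treatment assignment". The same section says that "all follow-up visits and endpoint adjudications will be performed by a dedicated study nurse blinded to treatment allocation".
- **Who judges relatedness.** The only stated source is in SAP, Plan for Presenting Data to DMC: "incidence rates for AE and SAE will be analyzed by investigator attributed relatedness and severity of the events". Protocol 4(f)(iv) adds that "a Clinical Events Committee (CEC) will be formed to adjudicate adverse events in the study". It describes this committee as independent of the Study Chair and Site Investigators, but does not say whether it is masked or whether its classification is the one analysed.
- **All events.** Protocol 4(f)(iv) collects every event, related or not. The DMC plan tabulates AEs and SAEs by arm with a p-value column.

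**The concern.** Whether an event enters this comparison depends on a causal judgement that can depend on knowing the arm. An ILLT patient's event can be put down to any of three exposures, an SMT patient's to two. The protocol's list of apheresis-related events, in 4(f)(ii), includes chest pain, nausea, headache, tachycardia and shortness of breath, which can also follow an ACS and PCI without apheresis. The bar is low, because any reasonable causal link makes an event at least possibly related.

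Two errors could follow. With equal true event rates, readier attribution in ILLT produces an apparent excess of harm. Alternatively, a real excess is lost, either because apheresis symptoms are put down to the ACS or because they are pooled with statin and catheterisation events common to both arms. Protocol 4(a) makes additional safety data on post-PCI apheresis the safety objective, so both errors matter.

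**Working it through.** **Arm size.** The documents give no power or event rate for the AE/SAE comparison. They give N = 128 randomised 1:1, so 64 per arm. That total reproduces: a two-sided t-test at 0.05 with d = 0.65 and 90% power needs 51 per arm, and 102 / 0.8 = 127.5, rounded up to 128. It is not in dispute and serves only to fix the arm size.

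**Method.** Exact enumeration of two independent Binomial(64) counts x and y with the uncorrected Pearson chi-square test at two-sided 0.05. Reject if |z| > 1.96, where z = [(x − y)/64] / √[2p̄(1 − p̄)/64] and p̄ = (x + y)/128. All event and attribution rates below are assumptions.

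**Creating a difference.** The rate analysed is the true rate times the probability of being called attributable.

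| True rate, both arms | Called attributable, ILLT / SMT | Rates analysed | Rejection |
|---|---|---|---|
| 20% | 60% / 60% | 12% vs 12% | 4.9% |
| 20% | 60% / 40% | 12% vs 8% | 11.6% |
| 20% | 60% / 20% | 12% vs 4% | 39.5% |
| 30% | 60% / 40% | 18% vs 12% | 15.1% |
| 30% | 60% / 20% | 18% vs 6% | 56.5% |

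**The same case when pooled.** If the comparison is of any attributable event, and other attributable events affect a fraction b of both arms independently, each rate p becomes 1 − (1 − p)(1 − b). For 12% vs 4%:

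- b = 10%: 20.8% vs 13.6%, rejection 18.4%
- b = 20%: 29.6% vs 23.2%, rejection 13.2%
- b = 30%: 38.4% vs 32.8%, rejection 10.6%

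For 12% vs 8%, the same three values of b give 7.8%, 7.0% and 6.6%.

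**Hiding a difference by pooling.** Take an event caused only by apheresis, in 10% of ILLT and 0% of SMT, with perfect attribution:

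- alone: 10% vs 0%, detected 89.4% of the time
- b = 10%: 19% vs 10%, 29.7%
- b = 20%: 28% vs 20%, 18.5%
- b = 30%: 37% vs 30%, 13.7%

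**Hiding a difference by filtering.** A true all-event difference of 60% vs 35% has 80.6% power. If 30% of events are called attributable in each arm, the rates become 18% vs 10.5% and power is 22%.

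**Without the filter.** With equal true all-event rates of 30%, 50% or 70%, rejection is 5.1%, 4.5% or 5.1%, however relatedness is judged.

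**The case against.** The strongest reply is that the filtered comparison is only a supplement. A reader might infer that the final safety analysis rests solely on attributable events. The documents do not support that. The primary safety endpoint covers hypotension, ischaemia, bleeding, death and similar events over the PCI and apheresis period, and it is compared without a filter, as is MACE. The MCF and overall-profile comparisons state no filter and may cover all events. No stopping rule or success criterion depends on the filtered comparison. This stands and limits the point to the general AE/SAE incidence comparison.

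A reader might also infer that the final analysis is bound to use the unblinded investigator's attribution. That wording comes from the DMC section, and the final safety section names no one. A blinded nurse performs follow-up visits and an independent committee adjudicates adverse events. Their remits overlap without contradicting each other, and how to mask them is an operational choice. What remains is that no text assigns relatedness blind to arm.

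On pooling, the three-part definition is for safety monitoring, the protocol already sorts related events into three categories, and a similar analysis could be read as one run event type by event type. If so, the dilution figures do not apply and the unpooled figures do. The 39.5% and the dilution describe different readings and should not be claimed together. Finally, an added exposure in ILLT is part of the contrast under study, and events it causes are real harm. That is true, but it does not justify selecting events by a judgement that may depend on the arm.

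**Conclusion.** The point holds in this limited form. Beyond the named safety endpoints and MACE, the final safety section specifies an AE/SAE incidence comparison only for events judged attributable, and nothing says that judgement is blind to arm. Such a filter can bias the comparison in either direction.

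The size rests on assumed rates. With no true difference and a 60% / 20% attribution split of a symptom present in 20% of each arm, false rejection is 39.5% if the symptom is tested alone and about 11-18% if pooled with attributable events in 10-30% of both arms. A 60% / 40% split gives 11.6% alone and about 7-8% pooled. Detection of an apheresis-only event in 10% of ILLT falls from 89% to about 14-30% on pooling. The documents give no attribution rates, so these figures show what is possible and do not forecast what will happen. It should be corrected, but it does not undermine the named safety endpoints.

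**What to change.** In SAP, Analysis of Safety Outcomes, and Protocol 4(g)(vi):

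1. Make the between-arm incidence comparison and the MCF analysis cover all AEs and all SAEs by randomised arm, regardless of attribution. Count from randomisation, because collection starts at consent, before PCI.
2. Report attributable events as a secondary descriptive summary, split by the protocol's own categories: apheresis, statin, and follow-up catheterisation with IVUS-VH. State who assigned relatedness and whether they knew the arm.

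The cost is wording in two documents. The events are already collected, and all-AE/SAE tables by arm are already planned for the DMC. The downside is that an all-event comparison includes unrelated background events. It removes the dependence on attribution but can itself dilute an apheresis-specific effect, which is why the split summary is needed and why the existing event-type breakdown should be kept.

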## **Primary Safety Outcome Measure**

The primary safety outcome measures will be the total number of and percentage of patients with major peri-PCI procedure adverse events, such as hypotension, angina, myocardial ischemia, myocardial infarction (if the patient is determined to have had unstable angina rather than non-ST-elevation MI at admission), cerebrovascular event (CVA), vermicular tachycardia, bleeding (at the PCI access and apheresis cannulation sites in the apheresis patients and at the PCI access site in the non-apheresis control patients), and death. The peri-PCI procedure is defined as encompassing the time of the PCI procedure and the time of the subsequent LDL-apheresis procedure for ILLT group versus the time of the PCI procedure for SMT group. All LDL-apheresis-related adverse events in the ILLT group, including any minor expected events, will be recorded.

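### Safety is grouped only by randomised arm where a grouping is named, with no analysis by LDL-apheresis actually received; a small added table would give the risk per treated patient

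*SAP*

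**What the plan says.** **Objective.** Protocol 4(a) sets the safety objective in ACS patients who undergo LDL-apheresis after PCI. Protocol 1(b) hypothesises that major peri-PCI events will not be a safety concern.

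**Grouping.** Under Analysis of Safety Outcomes, the SAP says of safety profiles that they "will be compared for the two randomization groups including the times of event recurrence and censoring mechanisms". Protocol 4(g)(vi) uses the same grouping. The sentence closes the text on the mean cumulative function. For the crude incidence analysis the SAP says only that "the percentage of people who experience the event at least once will be compared using the chi-square test", without naming an analysis set. Intention-to-treat is stated for the effectiveness outcomes, not for safety.

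**Window.** The peri-PCI period for the primary safety endpoint covers the PCI and then "the time of the subsequent LDL-apheresis procedure for ILLT group versus the time of the PCI procedure for SMT group" (SAP, Primary Safety Outcome Measure; same definition in Protocol 4(b)). That section adds: "All LDL-apheresis-related adverse events in the ILLT group, including any minor expected events, will be recorded".

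**Attribution.** The SAP also plans that "a similar analysis will be done for all AE and SAE that are possibly or probably attributable to the study intervention". Protocol 4(f)(iv) gives that term a broad meaning: "the study intervention is defined as the use of 1) statins with or without the addition of LDL-apheresis, 2) LDL-apheresis", and, third, follow-up catheterisation with IVUS-VH.

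**Collection and deviations.** Protocol 4(f)(iv) states: "All AE/SAE/UADE including both those related to the study intervention and those not related to the intervention, will be collected and recorded". In Plan for Presenting Data to DMC, the SAP will report by treatment group "The number of patients who do not receive a study intervention, receive the wrong study intervention in error", as well as patients who intentionally receive the intervention they were not assigned. These counts are not linked to any safety denominator. The AE/SAE table shell there has ILLT and SMT columns only.

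**The concern.** The population in the safety objective is defined by receiving apheresis, yet no planned analysis uses that population.

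- An ILLT patient who never starts a session has no apheresis exposure but stays in the ILLT denominator. The ILLT rate is then an average over treated and untreated patients, and it falls below the rate per treated patient.
- An SMT patient who is given apheresis has, read literally, no apheresis window. An event during that session falls outside the primary safety endpoint and is tabulated under SMT.

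Keeping patients as randomised is usually the cautious choice for a superiority test. For harm per exposed patient it errs in the reassuring direction, and reassurance is what the safety hypothesis asks for. The attribution analysis does not close the gap, because its definition of the study intervention pools statins, apheresis and follow-up catheterisation.

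**Working it through.** **Inputs**

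| Input | Value | Source |
|---|---|---|
| Pivotal sample size | 128, 1:1, 64 per arm | Protocol 4 and 4(g)(ii) |
| Effect size, power, alpha, drop-out | d = 0.65, 90%, 0.05 two-sided, 20% | Protocol 4(g)(ii), 4(g)(ix); SAP, Sample Size Determination |
| Phase 1 apheresis event | 1 transient hypotension in 20 patients randomised to apheresis | Protocol 3(c) |
| ILLT patients not starting apheresis | not given; 5%, 10%, 20% of 64 assumed, about 3, 6, 13 patients | assumption |
| SMT patients given apheresis | not given; 0% to 5% assumed | assumption |
| Event rate per treated patient | 10% for illustration | assumption |

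**Step 1: the denominator.** A two-sample t-test with d = 0.65, two-sided alpha 0.05 and 90% power needs 51 per arm. Then 102 / 0.80 = 127.5, rounded up to 128. The plan's figure is reproduced, so the safety denominators are 64 per arm. The documents give no safety power or safety margin to reproduce.

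**Step 2: dilution in the ILLT arm.** Let k be the number of untreated patients, and assume they have no such events. As-randomised rate = 0.10 × (64 − k) / 64.

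- k = 3: 0.10 × 61/64 = 9.5%
- k = 6: 0.10 × 58/64 = 9.1%
- k = 13: 0.10 × 51/64 = 8.0%

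**Step 3: background risk.** The primary endpoint also counts events during the PCI, so untreated patients are not risk-free. With an assumed 5% risk in them, the rate is [0.10 × (64 − k) + 0.05 × k] / 64, which gives 9.8%, 9.5% and 9.0%. With k = 0 it is 10% and there is no dilution.

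**Step 4: general form.** Let f be the share of ILLT not starting apheresis, g the share of SMT given it, pa the risk with apheresis and p0 the risk without. Suppose events are ascertained alike in everyone and the risks do not otherwise differ by arm.

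- ILLT rate = (1 − f) pa + f p0
- SMT rate = (1 − g) p0 + g pa
- Difference = (1 − f − g)(pa − p0)

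For f = 5%, 10%, 20% the factor is 0.95, 0.90, 0.80 with g = 0, and 0.90, 0.85, 0.75 with g = 5%. This isolates dilution. It leaves out the unequal windows of the primary endpoint, so it is not an estimate of the net bias there.

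**Step 5: zero events.** The exact one-sided 97.5% upper limit for 0 of n is 1 − 0.025^(1/n).

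- n = 64: 5.6%
- n = 61: 5.9%
- n = 58: 6.2%
- n = 51: 7.0%

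The SAP plans no such limit. The figures show how the denominator would matter if one were reported.

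**Step 6: scale against sampling error.** For 6 events in 64 the exact 95% interval is 3.5% to 19.3%. For the phase 1 result of 1 in 20 it is 0.1% to 24.9%. The dilution in steps 2 and 3 is small beside these widths.

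**The case against.** **Analysis by randomised arm is legitimate.** The primary safety endpoint can be read as the risk of an assigned strategy. This stands, and the randomised comparison should stay.

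**Only the randomised comparison is planned.** A reader might infer that every safety analysis is restricted to randomised groups. The text does not go that far. The named grouping sits in the event-based text, and the chi-square and logistic analyses state no set. What the documents support is that the safety analysis set is undefined and randomised arm is the only grouping named.

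**Crossover events are lost.** A reader might infer that an apheresis event in an SMT patient is counted nowhere. That is not so. All adverse events are collected whatever their relation to the intervention. Protocol 4(f)(ii) has a category for events related to LDL-apheresis with no limit by arm, and the SAP tabulates by arm and attributed relatedness. The event is missed only by the primary safety endpoint.

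**Apheresis harm is biased low.** A reader might infer this for the arm comparison. The ILLT window is longer than the SMT window, which pushes the ILLT rate up, so the net direction is not established.

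**Non-receipt may be rare.** Two large-bore cannulas must be in place before randomisation (4(c)(ii)), complicated PCI and unstable patients are excluded (4(c)(iii)), and patients may decline after PCI before randomisation (4(c)(v)(2)). The ACE-inhibitor provision moves the apheresis timing and does not cancel the session. The limit of two patients per day in 4(i) caps enrolment together with treatment, and would hardly bind at 1.5 patients per site per month. Neither is evidence of non-receipt. The DMC reporting text provides for deviations without predicting them. All this stands, and it limits the likely size without supplying the missing analysis.

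**Conclusion.** The point holds as a cheap improvement. The safety objective is about patients who undergo apheresis. The documents name only randomised arm as a grouping, tie the apheresis window and the apheresis-event recording rule to ILLT, and plan no analysis by apheresis received. The opening part of the SAP was not available for this review, and nothing is inferred from it.

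The consequence is conditional. If some ILLT patients do not start apheresis, the as-randomised ILLT rate understates the risk per treated patient: under the assumptions in steps 2 and 3, by 0.5 to 2.0 percentage points on a 10% rate with no background risk, and by 0.2 to 1.0 points with a 5% background risk. If everyone assigned to apheresis receives it, the understatement is zero. All non-receipt rates are assumed. The conclusion concerns the rate per treated patient and does not extend to the direction of the between-arm primary safety comparison.

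**What to change.** Add to Analysis of Safety Outcomes in the SAP:

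1. State the analysis set for each safety analysis, including the chi-square and logistic ones, and keep the comparison by randomised arm.
2. Beside it, report apheresis-session events and apheresis-related adverse events among all patients in whom an LDL-apheresis session was started, whatever their assigned arm, with an exact confidence interval.
3. In Primary Safety Outcome Measure and Protocol 4(b), apply the apheresis window, and the rule on recording apheresis-related events, to any patient who receives apheresis.
4. Show the counts of non-receipt and crossover, already planned for the DMC, next to these tables.

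The cost is SAP and protocol wording and one extra table. The receipt data are already required for the DMC reports, and adverse events are already collected in all participants. The downside is that the table by treatment received is not protected by randomisation, so it should be labelled descriptive and read with the as-randomised table.
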